8. PHARMACOKINETIC ANALYSES

Concentrations of filgotinib and its metabolite GS-829845 in plasma will be determined using validated bioanalytical assays. Plasma PK parameters of filgotinib and GS-829845, will be evaluated.

8.1. PK Analyses Related to Intensive PK Sampling

Steady-state PK over a 24 hour dosing interval will be determined in subjects in the PK Substudy Analysis Set.

8.1.1. Estimation of Pharmacokinetic Parameters

PK parameters will be estimated using Phoenix WinNonlin[®] software using standard noncompartmental methods. The linear/log trapezoidal rule will be used in conjunction with the appropriate noncompartmental model, with input values for dose level, dosing time, plasma concentration, and corresponding real-time values, based on drug dosing times whenever possible.

All predose sample times before time-zero will be converted to 0. Predose samples may also serve as the 24-hr post dose sample if appropriate.

For area under the curve (AUC), samples BLQ of the bioanalytical assays occurring prior to the achievement of the first quantifiable concentration will be assigned a concentration value of 0 to prevent overestimation of the initial AUC. Samples that are BLQ at all other time points will be treated as missing data in WinNonlin. The nominal time point for a key event or dosing interval (τ) may be used to permit direct calculation of AUC over specific time intervals. The appropriateness of this approach will be assessed by the PK scientist on a profile-by-profile basis.

Pharmacokinetic parameters such as AUC_{τ} , λ_z and $t_{1/2}$ are dependent on an accurate estimation of the terminal elimination phase of drug. The appropriateness of calculating these parameters will be evaluated upon inspection of PK data on a profile-by-profile basis by the PK scientist.

8.1.2. Pharmacokinetic Parameters

PK parameters will be generated for all subjects in the PK Substudy analysis set. The analytes presented in [Table 8-1](#) will be evaluated if data are available.

Table 8-1. Study Treatments and Associated Analytes

Treatment	Analyte
Filgotinib 200 mg	Filgotinib, GS-829845
Filgotinib 100 mg	Filgotinib, GS-829845

The analytes and parameters presented in [Table 8-2](#) will be used to evaluate the PK objectives of the study. The PK parameters to be estimated in this study are listed and defined in the Pharmacokinetic Abbreviations section.

Table 8-2. Pharmacokinetic Parameters for Each Analyte

Analyte	Parameters
Filgotinib	AUC_{last} , AUC_{tau} , C_{tau} , C_{max} , T_{max} , C_{last} , T_{last} , λ_z , CL_{ss}/F , V_z/F , and $t_{1/2}$, if appropriate
GS-829845	AUC_{last} , AUC_{tau} , C_{tau} , C_{max} , T_{max} , C_{last} , T_{last} , λ_z , and $t_{1/2}$, if appropriate

In addition, molar ratio of metabolite to parent exposure (AUC_{tau} and C_{max}) may be calculated for individual subjects and summarized by treatment. The GS-829845 to filgotinib ratio for AUC_{tau} will be calculated by dividing the AUC_{tau} (in h*nmol/L) of GS-829845 by the AUC_{tau} (in h*nmol/L) of filgotinib. The GS-829845 to filgotinib ratio for C_{max} will be calculated by dividing the C_{max} (in nmol/L) of GS-829845 by the C_{max} (in nmol/L) of filgotinib.

8.1.3. Statistical Analysis Methods

Individual subject concentration data and individual subject PK parameters for filgotinib and GS-829845 will be listed and summarized using descriptive statistics by treatment. Summary statistics (number of subjects [n], mean, SD, coefficient of variation [%CV], median, minimum, maximum, Q1, and Q3) will be presented for both individual subject concentration data by time point and treatment; and individual subject PK parameters by treatment. Moreover, the geometric mean, 95% CI, and the mean and SD of the natural log-transformed values will be presented for individual subject PK parameter data.

[figure not shown]
Individual concentration data listings and summaries will include all subjects with concentration data. The sample size for each time point will be based on the number of subjects with nonmissing concentration data at that time point. The number of subjects with concentration BLQ will be presented for each time point. For summary statistics, BLQ values will be treated as 0 at predose and one-half of the lower limits of quantitation (LLOQ) for postdose time points.

Individual PK parameter data listings and summaries will include all subjects for whom PK parameter(s) can be derived. The sample size for each PK parameter will be based on the number of subjects with nonmissing data for that PK parameter.

The following tables may be provided for each analyte by treatment:

- Individual subject concentration data and summary statistics
- Individual subject plasma PK parameters and summary statistics.

The following figures may be provided for each analyte by treatment (for PK substudy only):

Individual, mean, and median postdose concentration values that are \leq LLOQ will not be displayed in the figures and remaining points connected.

The following listings may be provided:

- PK sampling details (and PK concentrations) by subject, including procedures, differences in scheduled and actual draw times, and sample age
- Individual data on determination of plasma half-life and corresponding regression correlation coefficient.

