3.2. Study Design

This is a randomized, double-blind, placebo- and active-controlled, Phase 3 study in adult male and female subjects with active RA who have an inadequate response to MTX. The study is designed to evaluate the efficacy, safety and tolerability of filgotinib as well as its effect on patient-reported outcomes, including work productivity, fatigue, and quality of life. In addition, PK will be assessed.

Adult male and female subjects with active RA will be screened to determine eligibility as per the inclusion and exclusion criteria (see Section 4.2 and 4.3, respectively). The Screening period will be up to 28 days. The screening window may be extended to up to 42 days prior to the Day 1 visit for subjects who require repeat collection of radiographs.

Written informed consent must be obtained before any study-related procedures take place. During the Screening period, following signing of the informed consent form (ICF), radiographs (hands, wrists, and feet) will be sent for central review for confirmation of the number of documented joint erosions. Note that radiographs need to be sent for central review as soon as possible after capture and prior to Day 1 to allow for central reading and confirmation of the joint erosions for eligibility purposes.

Subjects will be randomized in a 3:3:2:3 ratio to filgotinib 200 mg, filgotinib 100 mg, active comparator (adalimumab), or matching placebo controls administered for up to 52 weeks in a double blind fashion.

At Week 14, subjects who have not achieved a 20% improvement from Day 1 in both swollen joint count (SJC) and tender joint count (TJC) will discontinue investigational therapy but will continue with study visits and assessments per protocol. All subjects who discontinue from investigational therapy, are to receive standard of care treatment for their RA as determined by the investigator. At Week 24 all subjects assigned to placebo + MTX will be reassigned 1:1 to either filgotinib 100 mg q.d. or 200 mg q.d. in addition to MTX in a blinded fashion and will continue the study through Week 52.

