6.8. Pharmacokinetics Assessments

For all subjects, blood samples for PK analysis should be collected at least 30 minutes post study drug dosing at Week 4, prior to study drug dosing at Week 12 and Week 24, and any time at Week 52 or ET.

CCI

Plasma concentrations of filgotinib and GS-829845 will be analyzed.

Additional analyses (eg, for MTX and its metabolites, adalimumab) may be performed.

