8.7. Pharmacokinetic Analysis

Plasma concentrations of filgotinib and its metabolite (GS-829845) will be listed and summarized for all subjects by treatment using descriptive statistics (eg, sample size, arithmetic mean, geometric mean, % coefficient of variation, standard deviation, median, minimum, and maximum). **CCI**

Exposure-response analyses may be performed.

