3.1.5. Pharmacokinetic Analysis Set

The Pharmacokinetic (PK) analysis set includes all subjects in the Safety Analysis Set who have at least 1 nonmissing plasma concentration data for filgotinib and/or its metabolite GS-829845. This is the primary analysis set for general PK analyses.

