3.2. Subject Grouping

For analyses based on the All Randomized Analysis Set and FAS, subjects will be grouped according to the treatment to which they were randomized. For analyses based on the Safety Analysis Set and PP Analysis Set, subjects will be grouped according to actual treatment received. The actual treatment received will differ from the randomized treatment only when their actual treatment differs from randomized treatment for the entire treatment duration of each treatment period.

The treatment groups during the placebo controlled period are:

- Filgotinib 200 mg q.d.
- Filgotinib 100 mg q.d.
- Adalimumab
- Placebo

The treatment groups during the re-randomized period are:

- Filgotinib 200 mg q.d.
- Filgotinib 100 mg q.d.
- Adalimumab
- Placebo switch to filgotinib 200 mg q.d.
- Placebo switch to filgotinib 100 mg q.d.

For the PK Analysis Set, subjects will be grouped according to the actual treatment they received.

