3.8.2. Analysis Visit Windows

Subject visits may not occur on protocol-specified days. Therefore, for the purpose of analysis, observations will be assigned to analysis windows.

In general, the baseline value will be the last nonmissing value on or prior to the first dose date of study drug, except for the mTSS baseline value. The mTSS baseline value will be derived based on the measurements collected on or prior to the first dose date of study drug + 14 days given the potential delay in scheduling an x-ray assessment. If multiple valid, nonmissing measurements exist in the analysis window as aforementioned, in general, the last nonmissing mTSS value on or prior to the first dose date of study drug will be selected as the baseline value; If all these multiple measurements occur at post first dosing, the value closest to the first dose date will be selected as the baseline value.

For subjects who were on placebo and then re-randomized, the baseline after Week 24 will be the last nonmissing value obtained on or prior to the first dose date of filgotinib, except for the mTSS baseline value. The mTSS baseline value will be derived based on the measurements collected on or prior to the first dose date of filgotinib + 14 days given the potential delay in scheduling an x-ray assessment. If multiple valid, nonmissing measurements exist in the analysis window as aforementioned, in general, the last nonmissing mTSS value on or prior to the first dose date of filgotinib will be selected as the baseline value; If all these multiple measurements occur at post first dosing of filgotinib, the value closest to the first dose date of filgotinib will be selected as the baseline value.

For efficacy endpoints, vital signs, ECG, weight, lipids and safety laboratory data, the analysis visit windows will be applied to data collected during the ‘on-treatment’ period. The ‘on-treatment’ period is defined as the last dose date of any study drug + 7 days.

The analysis windows for on-treatment efficacy endpoints including joint count assessment, HAQ-DI (including subject’s pain assessment), subject’s global assessment (SGA), physician’s global assessment (PGA), serum CRP , exploratory patient reported outcome (PRO), and vital signs, weight, and safety laboratory data (lipid data excluded) are provided in [Table 3-1](#) and [Table 3-2](#).

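### No rule keeps samples drawn after filgotinib has been stopped out of the Week 24 and Week 52/ET concentration summaries

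*SAP*

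**What the plan says.** **Who is sampled.** Protocol 6.8 schedules PK blood for all subjects: at least 30 minutes after dosing at Week 4, and then "prior to study drug dosing at Week 12 and Week 24, and any time at Week 52 or ET". Appendix 2 (footnote o) narrows the Week 12 and 24 draws to the 2 hours before the dose.

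**Who stops drug and stays.** Under protocol 3.2, subjects who miss the Week 14 joint-count improvement "will discontinue investigational therapy but will continue with study visits and assessments per protocol". The same applies to those with confirmed loss of response from Week 30. Section 3.5.2 encourages subjects who stop permanently for other reasons to remain in the study, pregnancy excepted.

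**Who is summarised.** SAP 8.1.3 gives concentration statistics by time point and treatment and adds: "Individual concentration data listings and summaries will include all subjects with concentration data". Protocol 8.7 says plasma concentrations "will be listed and summarized for all subjects by treatment using descriptive statistics". The PK Analysis Set (SAP 3.1.5) takes in Safety Analysis Set subjects "who have at least 1 nonmissing plasma concentration data for filgotinib and/or its metabolite GS-829845", with no condition on when the sample was drawn. SAP 3.2 adds: "For the PK Analysis Set, subjects will be grouped according to the actual treatment they received".

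**What is restricted.** SAP 3.8.2 confines its visit windows to an on-treatment period that ends 7 days after the last dose of any study drug, and names the data it covers: "For efficacy endpoints, vital signs, ECG, weight, lipids and safety laboratory data, the analysis visit windows will be applied to data collected during the". Concentrations are not on that list.

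**Exposure-response.** Protocol 8.7 says only: "Exposure-response analyses may be performed". Neither document names a model, exposure measure, time point or dataset.

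**The concern.** A subject on filgotinib 200 mg who stops at Week 14 is still a filgotinib 200 mg subject under grouping by treatment received. If blood is drawn at Week 24, the result describes someone about 10 weeks off drug, yet it counts towards the 200 mg Week 24 predose summary, and again towards Week 52. Subjects who lose response later add to the Week 52 figure. The table would be read as exposure on the dose when it is a mixture of exposure and discontinuation.

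The mixing is also not random. Subjects leave drug at Week 14 because they did not respond. If these concentrations were later related to outcome, low concentration and poor response would go together even if exposure had no effect within a dose group.

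**Working it through.** The documents state no figure on this point, so there is nothing to reproduce.

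**Step 1. What an off-drug sample contains.** Week 14 to Week 24 is 10 weeks, or 70 days. The human half-life is not given. Even an assumed half-life of 7 days gives 70/7 = 10 half-lives, leaving 2^-10, about 0.1%, of the starting level. Treating the value as near zero is reasonable.

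**Step 2. Effect on the arithmetic mean.** Let M be the on-drug mean, q the share of samples drawn off drug, and c the value assigned to them:

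mean of all samples = (1 - q)M + qc

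- With c = 0 (the SAP 8.1.3 value for a predose BLQ result), the relative change is -q.
- With c = LLOQ/2 and an assumed LLOQ of 0.1M, c = 0.05M and the change is -0.95q.

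The counts below assume that all 450 planned subjects in a filgotinib group give a sample.

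| q | Off-drug samples of 450 | Change, c = 0 | Change, c = LLOQ/2 |
|---|---|---|---|
| 5% (assumed) | about 22 | -5.0% | -4.8% |
| 10% (assumed) | 45 | -10.0% | -9.5% |
| 20% (assumed) | 90 | -20.0% | -19.0% |
| 31.4% (rough ceiling, 200 mg) | 141 | -31.4% | -29.8% |
| 36.5% (rough ceiling, 100 mg) | 164 | -36.5% | -34.7% |

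The last two rows use protocol Table 1-1. Week 12 ACR20 non-response was 1 - 59/86 = 31.4% at 200 mg once daily and 1 - 54/85 = 36.5% at 100 mg once daily. Anyone who fails the joint-count check also fails ACR20 at that visit, so these rates roughly bound stops under the Week 14 rule. They come from another trial and a visit two weeks earlier, and they do not bound stops for other reasons.

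**Step 3. Effect on the median.** With off-drug values at the bottom of the distribution, the pooled median is the on-drug value at percentile (0.5 - q)/(1 - q). At q = 10% that is 0.40/0.90 = 44th; at q = 20% it is 0.30/0.80 = 37.5th. The median moves too, though how far in concentration units depends on the spread.

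**Step 4. If an exposure-response analysis used these samples.** A simulation took 450 subjects in one dose group with no true link, log-normal concentrations (log SD 0.6), a 60% on-drug response rate, and off-drug subjects set to concentration 0 and non-response. It used a rank test at 0.05 and 500 runs. The test was positive in 55% of runs at q = 5%, 98% at 10% and 100% at 20%. Restricted to on-drug samples, it was positive in about 4 to 5%. These settings are illustrative and are not taken from the plan.

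**Step 5. BLQ rules side by side for a Week 12 or 24 predose sample.**

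- SAP 8.1.3: 0 at predose.
- Protocol 8.3: 0 only before the first dose, otherwise half the LLOQ.
- SAP 3.7: 0 at predose and half the LOQ at postbaseline. These samples are both. The section also calls for log transformation of concentrations, which a 0 does not allow.

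**The case against.** **The sentence sits under intensive PK.** SAP 8.1 opens with steady-state sampling in the substudy, and the PK parameters come only from that substudy. This stands for the parameters. It does not stand for concentrations: within 8.1.3 only the figures are limited to the substudy, SAP 3.1.5 defines a set for general PK analyses, and protocol 8.7 covers all subjects.

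**Off-drug subjects may never be sampled.** The Week 24 draw is anchored to a dose that a stopped subject does not take. This stands in part, because neither document confirms that such draws are made. But the footnote sets timing and exempts nobody, whereas the protocol does state a waiver for early-termination X-rays. The Week 52/ET sample has no dose anchor at all.

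**The dilution would be visible.** SAP 8.1.3 reports the number BLQ per time point, along with the median and quartiles, and allows listings of scheduled against actual draw times. This helps a careful reader, but it corrects none of the statistics and does not separate off-drug samples from low on-drug troughs.

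**Week 52 is a poor exposure measure anyway.** Draws at any time of day mix times since dose even in fully dosed subjects. This is true and limits what is lost there; the Week 24 predose summary is the one that matters more.

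**Conclusion.** The point holds as a gap in the inclusion rule. As written, the plan admits post-discontinuation samples to the Week 24 and Week 52/ET concentration summaries by dose. If they are drawn, the arithmetic mean is low by about q. The size rests on an assumed q and, where half the LLOQ is used, on an assumed LLOQ. The damage is confined to descriptive tables: Weeks 4 and 12 are untouched by the Week 14 stop, and no efficacy hypothesis uses concentrations.

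Three stronger conclusions that a reader might draw are not supported:

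- **That the plan creates a false exposure-response link.** Such analyses are optional and unspecified, so Step 4 describes a conditional risk.
- **That off-drug values certainly enter the means.** Sampling after the stop is implied, not confirmed.
- **That geometric means would fall by a stated larger factor.** SAP 8.1.3 lists the geometric mean for PK parameters, not concentrations, and sets predose BLQ values to 0. Protocol 8.7 names the geometric mean only as an example.

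**What to change.** 1. In SAP 3.1.5 and 8.1.3, limit concentration summaries to samples taken on drug. Base the flag on the recorded last-dose date, which SAP 3.8.1 already derives for each study drug separately. The filgotinib date is the relevant one, and the allowed gap should be stated. Use time since last dose only where dose times are recorded; the documents do not show that prior-dose times are collected for these samples, so a rule in hours may not be workable.
2. Keep post-discontinuation samples in the listings only, flagged.
3. For placebo subjects reassigned at Week 24, assign each sample to the treatment being taken when it was drawn.
4. Apply the same restriction to any exposure-response analysis that is carried out.
5. State one BLQ rule for Week 12 and 24 predose samples and align SAP 3.7, SAP 8.1.3 and protocol 8.3 with it.

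The cost is SAP wording and one derived variable. Slightly fewer samples are summarised at Weeks 24 and 52.

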9. BIOMARKER ANALYSIS

A separate biomarker analysis plan (BAP) will document methods to analyze biomarker assessments.

11. SOFTWARE

SAS® Software Version 9.4. SAS Institute Inc., Cary, NC, USA.

nQuery Advisor(R) Version 4.0. Statistical Solutions, Cork, Ireland.

12. SAP REVISION

Revision Date (DD MMM YYYY)	Section	Summary of Revision	Reason for Revision
27 Nov 2018	Throughout the document	Editorial changes	Clarification
27 Nov 2018	Section 3.5	Update hierarchy list	Reflect endpoints importance
27 Nov 2018	Section 6.1	Estimands	Add definition of estimands
27 Nov 2018	Section 6.3.3	Non-inferiority sensitivity analysis	Add MI and TP analysis for non-inferiority tests
15 Jan 2018	Throughout the document	Editorial changes	Clarification

13. APPENDIX

Appendix 1. Lists of RA Medications

1) List of bDMARDs and Investigational bDMARDs (WHO Preferred Terms)

- ABATACEPT
- ADALIMUMAB
- CABIRALIZUMAB
- CERTOLIZUMAB
- CERTOLIZUMAB PEGOL
- CLAZAKIZUMAB
- DENOSUMAB
- ETANERCEPT
- GOLIMUMAB
- INFLIXIMAB
- INTERLEUKIN-2
- SIRUKUMAB
- TOCILIZUMAB

2) List of Oral Corticosteroids (WHO Preferred Terms)

- BETAMETHASONE
- BETAMETHASONE SODIUM PHOSPHATE
- CORTISONE
- DEXAMETHASONE
- DEXAMETHASONE PALMITATE
- DEXAMETHASONE PHOSPHATE
- DEXAMETHASONE SODIUM PHOSPHATE

- MEPREDNISONONE
- METHYLPREDNISOLONE
- METHYLPREDNISOLONE ACETATE
- METHYLPREDNISOLONE SODIUM SUCCINATE
- MOMETASONE FUROATE
- PREDNISOLONE
- PREDNISOLONE FARNESYLATE
- PREDNISONONE
- STEROIDS

3) List of Anti-malarials (WHO Preferred Terms)

- CHLOROQUINE
- CHLOROQUINE PHOSPHATE
- CHLOROQUINE SULFATE
- HYDROXYCHLOROQUINE
- HYDROXYCHLOROQUINE SULFATE

Appendix 2. Health Assessment Questionnaire Disability Index (HAQ-DI)

The HAQ-DI score is defined as the average of the scores of eight functional categories (dressing and grooming, arising, eating, walking, hygiene, reach, grip, and other activities), usually administered by the subject. Responses in each functional category are collected as 0 (without any difficulty) to 3 (unable to do a task in that area), with or without aids or devices.

The highest score for questions in each category (range 0 to 3) determines the score for the category, unless aids or devices are required. Dependence on equipment or physical assistance increases a lower score (ie, scores of 0 or 1) to the level of 2 to more accurately represent underlying disability. The eight category scores are averaged into an overall HAQ-DI score on a scale from 0 (no disability) to 3 (completely disabled) when 6 or more categories are non-missing. If more than 2 categories are missing, the HAQ-DI score is set to missing. The HAQ-DI can be treated as a continuous measure.

The HAQ-DI score using aids (and/or devices) is computed by taking the maximum score of the questions in each category (range: [0, 3]) and whether or not aids/devices are used (0 or 1):

$$A = \begin{aligned} & \max(\text{dressing \& grooming category questions, } 2 * \text{aids indicator}) + \\ & \max(\text{rising category questions, } 2 * \text{aids indicator}) + \\ & \max(\text{eating category questions, } 2 * \text{aids indicator}) + \\ & \max(\text{walking category questions, } 2 * \text{aids indicator}) + \\ & \max(\text{hygiene category questions, } 2 * \text{aids indicator}) + \\ & \max(\text{reach category questions, } 2 * \text{aids indicator}) + \\ & \max(\text{grip category questions, } 2 * \text{aids indicator}) + \\ & \max(\text{usual activities category questions, } 2 * \text{aids indicator}) \end{aligned}$$

$$\text{HAQ-DI} = A / (\text{total number of categories with at least 6 non-missing})$$

The following table shows the contribution of the 43 questions used to calculate the HAQ-DI:

HAQ-DI Category:	Category questions: At least 6 categories must have scores to compute the HAQ-DI.		HAQ-DI Category Score with Aids/Devices Calculation:
	Category Questions	Aids/Devices Indicators	
Dressing / Grooming	HAQ0101, HAQ0102 (DRESS, HAIR)	HAQ0114, HAQ0119 (DRSG, GROOM)	
Using each question with a scale of 0-3, calculate the category score as the maximum of the category questions.
 
If the Aids/Devices indicator is “No”, no need to adjust the category score.
 
If the Aids/Devices indicator is “Yes” and the category score is <2, then the category score with the Aids/Devices is set to 2.
 
If the Aids/Devices indicator is “Yes” and the category score is ≥2, then the category score with Aids/Devices is the calculated category score without adjustment.
 
For example: The Dressing/Grooming category score is 2 if subject answered 1 for both questions 1 and 2 and “Yes” for both question 14 and 19.
 
In the HAQ-DI score calculation, questions on other device/aids will not be used.

Arising	HAQ0103, HAQ0104 (STAND, BED)	HAQ0116, HAQ0120 (CHAIR, ARISING)	
Eating	HAQ0105, HAQ0106, HAQ0107 (MEAT, LIFT, MILK)	HAQ0115, HAQ0121 (UTENSIL, EAT)	
Walking	HAQ0108, HAQ0109 (WALK, STEPS)	HAQ0110, HAQ0111, HAQ0112, HAQ0113, HAQ0122 (CANE, WALKER, CRUTCH, WHEEL, WALKING)	
Hygiene	HAQ0123, HAQ0124, HAQ0125 (WASH, BATH, TOILET)	HAQ0134, HAQ0135, HAQ0137, HAQ0139, HAQ0142 (RAISEAT, BATHBAR, BATHSEAT, LONGBATH, HYGIENE)	
Reach	HAQ0126, HAQ0127 (REACH, BEND)	HAQ0138, HAQ0143 (LONGRCH, REACH)	
Grip	HAQ0128, HAQ0129, HAQ0130 (OPENCAR, JAR, FAUCET)	HAQ0136, HAQ0144 (JAROPEN, GRIP)	
Activity	HAQ0131, HAQ0132, HAQ0133 (SHOP, INCAR, CHORES)	HAQ0145 (ERRAND)	

Handling Missing Data: If no more than 2 categories have missing category scores, then the HAQ-DI is the mean of the non-missing category scores. Otherwise, the HAQ-DI score is set to missing.

If any of the category questions are missing, but the aids/device indicator is non-missing, the category score can still be computed. However, if all category questions and its aids/device indicators are missing, then the category score is considered missing.

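### Read literally, SAP Appendix 2 can score an unanswered HAQ-DI category as 0 when the aids indicator is 'No', while other text in the same appendix implies no score

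*SAP*

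**What the plan says.** SAP Appendix 2 describes the HAQ-DI category score in three ways.

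- **Formula.** "The HAQ-DI score using aids (and/or devices) is computed by taking the maximum score of the questions in each category", compared with twice an aids indicator coded 0 or 1. The eight category values are summed and divided by the number of categories available.
- **Narrative and table.** The narrative lets the highest question score determine the category, and need for aids or help lifts a score of 0 or 1 to 2. The table tells the programmer to "calculate the category score as the maximum of the category questions" and to leave that score alone when the aids indicator is 'No'.
- **Missing-data rule.** "If any of the category questions are missing, but the aids/device indicator is non-missing, the category score can still be computed". The only stated condition for a missing category is the next sentence: "if all category questions and its aids/device indicators are missing, then the category score is considered missing".

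There is also an overall safeguard: "If more than 2 categories are missing, the HAQ-DI score is set to missing".

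**The concern.** The case in question is a category in which the subject answers no question but the aids indicator is recorded as 'No'. The formula and the missing-data rule together return 0, so an absent answer becomes the most favourable one. The narrative and table leave nothing to score. Two programmers following the same appendix could derive different HAQ-DI values from the same questionnaire.

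HAQ-DI change at Week 12 is the second and third test in the hierarchy (SAP Section 3.5). HAQ-DI is one of the five ACR20 items of which three are needed (SAP Section 6.2.1), and it defines the responder endpoint of a decrease of at least 0.22 (SAP Section 6.4).

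The multiple imputation and tipping point analyses in SAP Section 6.3.3.2 act on missing scores. A derived 0 is not missing, so it would pass through them as observed data. Scoring a blank as best is also out of line with the rest of the SAP. Joint counts and FACIT-Fatigue are prorated when at least half the items are present (Sections 6.1.1 and 6.3.1.4), and DAS28(CRP) is missing if any component is missing (Section 6.3.1.1).

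**Working it through.** **Inputs, all from SAP Appendix 2 unless noted.** Category = max(questions, 2 × aids), with aids = 0 or 1. HAQ-DI = mean of the non-missing categories, with at least 6 of 8 required. Responder threshold 0.22 (Section 6.4). ACR20 item threshold 20% (Section 6.2.1).

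**Reproducing the plan's example.** Answers 1 and 1 with aids 'Yes': max(1, 1, 2 × 1) = 2. This matches the appendix.

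**The same formula with questions unanswered**, taking the maximum over whatever is non-missing:
- no answers, aids 'No': max(2 × 0) = 0
- no answers, aids 'Yes': max(2 × 1) = 2
- no answers, aids missing: missing
- one answer of 1, the rest blank, aids 'No': max(1, 0) = 1

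The last line shows that the rule is harmless when at least one question is answered. The problem is confined to the first line.

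**Size per post-baseline blank.** Replacing a true category score s by 0 lowers the mean of eight by s/8: 0.125 for s = 1, 0.25 for s = 2, 0.375 for s = 3. One blank with s of 2 or 3 exceeds 0.22 alone.

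**Illustration: every category truly 2 at baseline and Week 12, no real change, blanks at Week 12 with aids 'No'.**

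| Blank categories | Literal HAQ-DI | Apparent improvement | Blank treated as missing |
|---|---|---|---|
| 1 | 14/8 = 1.750 | 0.250 (12.5%) | 2.000 |
| 2 | 12/8 = 1.500 | 0.500 (25.0%) | 2.000 |
| 3 | 10/8 = 1.250 | 0.750 (37.5%) | HAQ-DI missing |
| 8 | 0/8 = 0 | 2.000 (100%) | HAQ-DI missing |

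The last two rows show the six-category minimum being bypassed.

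**ACR20 item.** With no real change, one blank reaches 20% only if s is at least a fifth of the sum of the eight category scores, for example 3/15 or 2/10. For the profile 3, 2, 2, 2, 2, 2, 1, 1 (sum 15) with the 3 left blank, the literal rule gives 12/8 = 1.500 against 15/8 = 1.875, a drop of exactly 20.0%. Treating the category as missing gives 12/7 = 1.714, a drop of 8.6%. Averaging the remaining categories is therefore not free of error, but the error is smaller.

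**Blank at baseline.** With every category truly 2 and one blank at baseline, baseline is 14/8 = 1.75. An unchanged Week 12 score of 2.00 then reads as a worsening of 0.25.

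**The case against.** The strongest reply is that nowhere does the SAP say a blank category scores 0. The sentence about missing questions is most naturally about partial non-response, where taking the maximum of the answered items is sensible. The narrative and the table both treat aids as something that raises an existing score; with no answers there is nothing to raise. The six-category minimum appears more than once in the appendix, so a reading that defeats it is unlikely to be what the authors meant.

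This stands as far as intent goes: the 0 is derived, and the SAP does not define how the maximum treats missing arguments. It does not remove the problem, because the only stated condition for a missing category requires the aids indicators to be missing too. That condition makes sense for aids 'Yes', where the formula gives 2, but as written it does not separate 'Yes' from 'No'.

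The reply is also right that the harm depends on data conventions not given here. If an unticked aid is stored as missing, the category is missing and the problem largely disappears. If it is stored as 'No', categories would almost never be missing.

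A reader might go further and infer that blank categories inflate ACR20 and favour filgotinib. The documents do not support that. Only post-baseline blanks with a true score above 0 lower HAQ-DI, and baseline blanks push the other way. ACR20 changes only if the false drop carries the HAQ-DI item to 20%, both joint counts already qualify, and HAQ-DI is the deciding third item. The rule is the same in every blinded arm, and nothing indicates that blanks differ between arms. If blanks were equally frequent in both arms and unrelated to the scores, the literal rule would multiply both Week 12 means by the same factor below 1, which shrinks the difference.

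**Conclusion.** The point holds as an unreconciled rule in Appendix 2: for a category with no answers and aids 'No', the formula plus the missing-data sentences give 0, and the narrative and table give no score. On the literal reading, the error per affected post-baseline category is s/8 (0.125 to 0.375 for s of 1 to 3), a baseline blank produces the opposite error, and an entirely blank questionnaire with aids 'No' gives a HAQ-DI of 0.

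These sizes are per subject and rest on illustrative profiles. The effect on the treatment comparison cannot be computed from the documents and may be small; no bias between arms is shown. The correction is still worth making: HAQ-DI feeds formal tests, the planned sensitivity analyses would not address a false 0, and the change is nearly free.

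**What to change.** Replace the two missing-data sentences in SAP Appendix 2 on category questions and aids indicators with:

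> If at least one category question is answered, the category score is the maximum of the answered questions, raised to 2 if aids is Yes and that maximum is below 2. If no category question is answered and the aids indicator is No or missing, the category is missing.

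Then state explicitly the result when no question is answered and aids is 'Yes' (the current formula gives 2), state whether an unticked aid is stored as 'No' or as missing, and apply the at-least-six-categories rule last.

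The cost is a few lines of text and one condition in the derivation program. A blinded count of categories with no answers and aids 'No', by visit, would show whether any subject is affected. SAP Section 1 places finalization before the Week 24 unblinding, so the change belongs there; if made later, the same section requires it to be documented in the study report.
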